5.6 Participant Compensation

Participants will not receive compensation as the study does not require any additional expense beyond standard clinical care.

5.7 End of Study

The end of study is the completion of all final monitoring and data collection.

3. Statistics and Analysis

6.1 Data Analysis

Qualitative Study

Interview data will be analysed using Reflexive Analysis as outlined by (Braun & Clarke, 2006; Braun & Clarke, 2019; Braun & Clarke, 2020). Reflexive Analysis begins with the recognition that any clinical researcher will have biases that cannot be controlled for, but which should be understood and built into the generation of data when interpreting interview data. This data will help us explore the complex and contributing factors making up parental viewpoints around the success of ECHO. It will allow us to understand which themes need to be captured in outcome measures for later iterations of this programme development, ar it will support participant partnership in intervention development.

The Speech and Language Therapist (SLT) that conducted the interview will ensure that the participant's identity is protected within any stored data. The study will comply with the Data Protection Act which requires data to be anonymised as soon as it is practical to do so. Transcripts will be checked by another member of the research team. Once the transcript is finalised and pseudonymised, audio files will be stored as source data in secured folders with access restricted to study research members on MFT servers. Only pseudonymised transcript data will be shared for analysis.

Reflexive Analysis will be led by the SLT researcher with contributions in multiple key ways from the wider research team. This will ensure reflexive practice and careful consideration of theme generation. In the first instance, the team will independently undertake a deep reading of a first chosen transcript. Then, they will perform a line-by-line analysis, assigning preliminary codes and highlighting potential themes in the data, again independently. They will come together in a first meeting to discuss their finding and contribute to a shared understanding of the first transcript. A preliminary manual coding frame will result from this meeting, which can then be applied to a second transcript, again independently reviewed by Protocol V.1.1 Date: 16.05.2024 IRAS ID: 331323 24

Manchester Local Care Organisation MANCHESTER CITY COUNCIL

Department for Education

Manchester University NHS Foundation Trust

the research team. A second meeting will be held to discuss changes to the coding frame resulting from the second transcript. In a third round of coding the team will attempt to fit the new coding frame to a third paper. A third meeting will bring together the team's thoughts on the existing coding frame, and how those codes might best be hierarchically organised. At this point, the lead SLT researcher will continue the analysis, by applying the coding frame to the remaining transcripts. It is possible that further iterations of the codes or thematic structure may occur after this point, taking into account findings from the different interviews. Changes will be made in email correspondence with the team until it is agreed that the frame is a good fit for all the data.

Prototypical quotes will be collected to exemplify the meaning of the code. These quotes will represent an array of participants. A member of the team will perform a final validity check of the table of themes, codes, and associated quotes. Findings will be reported in line with APA standards (Levitt, 2019).

ECHO Intervention Study

All variables will be presented with appropriate descriptive statistics and graphics to examine for completeness and form. No imputation will be made for missing data, but in the event of larger numbers, sensitivity analyses may be utilised. The study will present the mean (SD), median (IQR), and counts (%) of baseline demographics.

The primary outcome will be reported at baseline and endpoint timepoints, alongside the change from baseline using appropriate descriptive statistics such as mean, median and SD/IQR. A paired t-test or Wilcoxon signed rank test as appropriate will be used to assess the difference between baseline and endpoint.

The quantitative secondary measures, the TOPSE, and parent-child interaction clinical measures will be presented as an overall score, with appropriate descriptive statistics at baseline and the endpoint. The TOPSE will be scored according to validated methods described in the TOPSE Manual (Bloomfield et al., 2010) and the parent-child interaction clinical measure will be scored according to current clinical practice. Differences between the two timepoints will be examined using paired t-tests or Wilcoxon signed-rank tests. Exploratory analyses will also examine these measures at an item level to identify any responses where the difference in scores between baseline and review is distinctive compared to other items in that measure. Boxplots will be used to illustrate the spread of the differences for each item.

WellComm Screen results will be presented as the number and percentage (with 95% binomial confidence intervals) of children who score Red, Amber, and Green at review. All children will score Red at baseline as this is part of the eligibility criteria. Children scoring Amber or Green at review indicates that they have made clinically significant progress as Red indicates significant language difficulties, Amber indicates mild to moderate language difficulties, and Green indicates no language difficulties.

The Pragmatics Profile provides qualitative data consisting of parents' descriptions of their child's communication which will be analysed using the descriptive method as recommended by the Pragmatics Profile manual (Pragmatics Profile of Everyday Communication Skills).

Confounding variables such as maturation effects cannot be controlled for in this study and any significant effects identified will need to be further studied in a randomised control trial to

Date: 16.05.2024

control for confounding variables. This analysis is therefore to be considered as hypothesis generating.

2. Ethical and Regulatory Considerations

7.1 Risks and Burdens to Participants and Researchers (if applicable depending on the study intervention)

Families participating in the study will receive the same intervention and number of visits as families not participating in the study as the study aims to assess the effectiveness of standard clinical care. Participants should not be at any increased risk compared to families accessing standard clinical care outside of the study.

The ECHO Distress Protocol in the ECHO Intervention Manual details procedures to follow in the event of any distress caused by the ECHO Intervention.

Families will be offered home visits, but alternative sites may be available if the family prefer or if there are concerns with visiting the home. Alternative sites include another home suggested by the family, or a children's centre. Virtual sessions may be offered if no suitable site can be found. Visits will be offered to accommodate families' working hours and children's schedules where possible.

Some families participating in this study may speak languages other than English. Outcome measures have all been reviewed to ensure that they can be used with families speaking languages other than English, and that they are culturally appropriate for families in Manchester. Outcomes measures will be evaluated for cultural and linguistic appropriateness at the point of data collection and any adaptations will be made in line with the published guidance for that outcome measure and recorded in the Case Report Form and deviation log. The ECHO Intervention was designed to be deliverable with interpreters and cultural sensitivity was considered in the design of the intervention.

The research team are equipped with lone worker devices and will follow MFT lone worker and home visiting safety protocols. The research team will maintain training on safeguardir. procedures in line with MFT mandatory training policies.

The study population will include families from a range of social-economic backgrounds. The research team are aware of local services available if families report financial or related barriers to participating in the study. Home visits are offered based on clinical knowledge that home visits are more accessible to many families in the target population.

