5.3 Sampling

5.3.1 Size of Sample

Qualitative Study

Data collection in the form of semi-structured in-depth interviews will be conducted until saturation of themes in the data collected is reached. It is expected that between 8-12 families will need to be interviewed to achieve saturation, based on similar literature (Neely et al., 2015; Thompson et al., 2017). This is consistent with the approach outlined in Braun and Clarke (2019).

ECHO Intervention Study

It is expected that 40 families will be recruited. This is a pragmatic sample size for an early exploratory study designed to generate hypotheses. The decision to target 40 families is based on prior experience with the intervention and considerations of time constraints, deeming it a realistic goal for recruitment. Allowing for 10% dropout, a medium effect size of 0.48 can be detected with alpha of 0.05 and 80% power. Assuming a clinical difference of 7, this equates to a standard deviation of 14.6.

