Withdrawals can either be made by the participant or the research team. Participants may withdraw from the study at any time, without giving a reason. The research team may withdraw a participant from the study for welfare or safeguarding reasons, if participation is no longer in their interest, or if contact for follow-up is lost for a prolonged period of time. The research team will complete a withdrawal form stating the date and reason for withdrawal. Data collected up until the point of withdrawal will be used unless participants request their data to be removed from the study. If participants request all data to be removed, this information will be deleted. Participants will not be replaced.

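### The paired tests and the WellComm colours at review describe only families who reach review, and the plan commits to no check on the 10% dropout it expects

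*Protocol*

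**What the plan says.** All references are to the Protocol.

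- **Section 6.1, primary outcome (CSBS DP).** "A paired t-test or Wilcoxon signed rank test as appropriate will be used to assess the difference between baseline and endpoint". Section 6.1 gives the same pair of tests for TOPSE and for the parent-child interaction measure.
- **Section 6.1, missing data.** "No imputation will be made for missing data, but in the event of larger numbers, sensitivity analyses may be utilised". It gives no number that counts as larger and names no method.
- **Section 6.1, WellComm.** The result is the "number and percentage (with 95% binomial confidence intervals) of children who score Red, Amber, and Green at review". The denominator is not stated. Every child is Red at baseline by eligibility, and Amber or Green at review is read as clinically significant progress.
- **Section 5.3.1.** The target is 40 families, and the precision claim reads: "Allowing for 10% dropout, a medium effect size of 0.48 can be detected with alpha of 0.05 and 80% power". The section then takes 7 points as the clinically relevant difference and derives an SD of 14.6 from it.
- **Section 5.5.** "Data collected up until the point of withdrawal will be used unless participants request their data to be removed from the study". Families who leave are not replaced.

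**The concern.** A paired test needs both scores. With no imputation, a family seen at baseline and not at review adds nothing to the estimate of change, although its baseline score is on file. For WellComm, a child not seen at review has no colour. To count that child as still Red would be a form of imputation, which 6.1 rules out, so a reviewed-only percentage is the natural reading even though the denominator is left open.

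The study has one arm, so the mean change and the share of children out of Red carry most of the quantitative message on child communication. Both would describe families who stayed. Section 5.5 lets families leave without giving a reason. It also lets the team withdraw them for welfare or safeguarding, because taking part no longer serves them, or after prolonged loss of contact. Some of these routes could plausibly be related to the child's progress. The limitations that the protocol names (convenience sampling, maturation and other confounding) do not cover attrition. Because the sensitivity analysis is optional and its trigger undefined, the plan can be followed to the letter at its expected dropout without anyone examining what that dropout does to the result.

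**Working it through.** **1. The plan's own figure.** Inputs from 5.3.1: 40 families, 10% dropout, alpha 0.05, power 80%, difference 7, SD 14.6.

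- Pairs left: 40 × 0.9 = 36.
- Paired t-test by the noncentral t distribution, two-sided 0.05, n = 36: the detectable standardised effect is 0.480, and power at 0.48 is 79.96%.
- 7 / 0.48 = 14.58, which rounds to 14.6.
- With 40 pairs the detectable effect would be 0.454; one-sided with 36 pairs it would be 0.423.

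The stated 0.48 is reproduced with 36 pairs, two-sided. The sample size thus already assumes that the primary test runs on families who reach review.

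**2. Mean change if leaving depends on baseline.** Assumptions that are not in the protocol: baseline and review scores are bivariate normal with equal variances; the correlation r is 0.3, 0.5 or 0.7; 4 of 40 leave, ranked on standardised baseline plus a standard normal noise term. From the protocol: change 7, SD of change 14.6. The SD at each visit is then 14.6 / √(2(1 − r)), or 12.3, 14.6 and 18.8 points.

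The expected error of the completers' mean change is −(1 − r) × (mean baseline of completers − mean baseline of all 40). I simulated 20,000 trials per setting.

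| r | Baseline gap, low scorers leave | Error, low scorers leave | Error, high scorers leave |
|---|---|---|---|
| 0.3 | 1.64 | −1.1 | +1.2 |
| 0.5 | 1.94 | −1.0 | +1.0 |
| 0.7 | 2.52 | −0.8 | +0.7 |

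Check at r = 0.5: −(1 − 0.5) × 1.94 = −0.97. Across settings the size is 0.7 to 1.2 points. With a standard error of about 2.4, that is 0.7/2.4 = 0.3 to 1.2/2.4 = 0.5 standard errors. Change is understated if low scorers leave and overstated if high scorers leave.

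The likelihood estimate on all 40 baselines is (completers' review mean) + b × (baseline mean of all − baseline mean of completers) − (baseline mean of all), where b is the completers' slope of review on baseline. Its error was under 0.04 in every setting, with the same standard error of about 2.4.

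**3. WellComm.** Illustration, not a forecast: 18 of 36 reviewed children are out of Red. Intervals are exact binomial 95%.

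- Reviewed only: 18/36 = 50% (32.9 to 67.1).
- All 40, unreviewed still Red: 18/40 = 45% (29.3 to 61.5).
- All 40, unreviewed all out of Red: 22/40 = 55% (38.5 to 70.7).

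The gap between the two bounds is 4/40 = 10 percentage points whatever the observed count.

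**4. Tipping point for the primary test.** The 36 completers have mean m and SD 14.6, and the 4 leavers are all set to a change of L. Combined mean = (36m + 4L)/40. Combined variance = [35 × 14.6² + 36 × (m − mean)² + 4 × (L − mean)²]/39.

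| m | Completers, p | L = 0: mean, p | L = −7: mean, p |
|---|---|---|---|
| 7 | 0.007 | 6.3, 0.007 | 5.6, 0.019 |
| 5 | 0.047 | 4.5, 0.048 | 3.8, 0.10 |

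Example, m = 5 and L = −7: SD 14.30, t = 3.8 / (14.30/√40) = 1.68, p = 0.10.

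**The case against.** A reader might infer that 6.1 contradicts 5.5, which promises to use data collected before withdrawal. The text does not support that. Section 5.5 is a rule on keeping and using data under consent. It does not say that such data enter the paired test. Section 6.1 presents descriptive statistics for all variables and reports the primary outcome at baseline, so leavers' scores are used there.

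A reader might also infer that the power statement is wrong, or that the result will be inflated. Neither follows. The 10% loss is built into the 36 pairs, and the direction of any error depends on who leaves.

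It can fairly be said that sensitivity methods and denominators often belong in an analysis plan, which is not at hand. That answers the bare absence of detail. It does not answer the rules that the protocol itself fixes: paired tests, no imputation, and a safeguard that is only optional.

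The figures have limits, and this part of the case against stands:

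- The dropout mechanism and the correlation are assumed. The model's near-zero error is expected, because the simulated data meet its assumptions.
- Setting all four leavers at −7 is an extreme. If they simply do not change, the p-value barely moves.
- The WellComm shift of 5 points either way lies well inside the reviewed-only interval of 33% to 67%.
- The protocol calls the study exploratory and hypothesis generating, and says that maturation cannot be controlled for.
- Counting unreviewed children as not progressed in the headline percentage would be single imputation. It belongs beside that percentage as a bound.

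**Conclusion.** The point holds as a modest analysis weakness. As written, 6.1 gives results for families who reach review, about 36 of 40 at the plan's expected dropout. It leaves leavers' baselines out of the estimate of change and commits to no examination of what dropout does.

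The likely size is small: about 0.7 to 1.2 points on a planned difference of 7, in either direction, if leaving depends on baseline and the correlation is 0.3 to 0.7. Ten percentage points of the all-enrolled WellComm result are undetermined when four children are not reviewed. A completer mean of 7 remains significant at the 0.05 level even in the extreme case shown; a completer mean of 5 does not. Higher loss would widen these ranges: 8 of 40 unreviewed leaves 8/40 = 20 points of WellComm open.

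The change is worth making because it is cheap and uses data already collected. It is not a condition for the study to be sound.

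**What to change.** Change section 6.1 as follows.

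1. Estimate mean change in CSBS DP, TOPSE and parent-child interaction with a likelihood-based repeated-measures model: visit as a fixed effect, unstructured covariance, fitted to every family with a baseline (apart from any who asked for their data to be removed). Keep the paired test as the completer analysis.
2. Keep the reviewed-only WellComm percentages and state their denominator. Show beside them the two all-enrolled bounds for the share out of Red: all unreviewed children still Red, and all unreviewed children out of Red.
3. Replace the optional, undefined sensitivity clause with a committed tipping-point analysis whenever any review is missing. Report the number of unreviewed families and their baseline scores.

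The cost is a few sentences and slightly more analysis. No new data, visits or families are needed. The model assumes that dropout is explained by observed scores, which is why the tipping-point analysis should go with it.

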Referrals received from health visiting service and/or children centre services. Eligibility and recruitment at initial visit.

Inclusion criteria: Parent/caregiver of child aged under 24 months at the start of intervention; Child Scored Red on WellComm Language Screen within 3 months of the referral; Child Scored High Likelihood of autism on Social Attention and Communication Surveillance (SACS-R) tool; Residing within the Manchester Local Authority for the duration of intervention.

Exclusion criteria: The family are currently receiving intervention from another Speech and Language Therapy Service; Parent/caregiver already taking part in the trial with another child; The child or parent has a diagnosis of visual, motor, or hearing impairment; The child has a diagnosis of a developmental disorder other than autism; Current significant and ongoing safeguarding concerns.

n = 40

Measures taken at baseline visit

Primary Outcome measure: The Communication and Symbolic Behaviour Scales Developmental Profile™ (CSBS DP)

Secondary Outcome measures:

The WellComm Language Screen; The Pragmatics Profile of Everyday Communication Skills; Clinical Outcome Measure Form (child's interaction, non-verbal communication skills, and language skills); The Tool to Measure Parenting Self-Efficacy (TOPSE); A research tool developed from local clinical service recording observations of parent-child interaction

5 ECHO intervention sessions delivered weekly

(Clinical outcome measure of parent-child interaction collected each session)

DEPENDED AND	
SR (#	
	100000
•	
10000	100
	100
10000	100
	-
	-
	-
10000	-
	-
	-
	-
	-
	-
	-
	-
	-
	-
	-
	-
	-
	-
	-
	-
	-
	-
	-
	-
	-
	-
	-

Measures taken 12 weeks following intervention

Primary Outcome measure: The Communication and Symbolic Behaviour Scales Developmental Profile™ (CSBS_DP)

Secondary Outcome measures:

The WellComm Language Screen; The Pragmatics Profile of Everyday Communication Skills; Clinical Outcome Measure Form (child's interaction, non-verbal communication skills, and language skills); The Tool to Measure Parenting Self-Efficacy (TOPSE); A research tool developed from local clinical service recording observations of parent-child interaction

1. Background

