3.2 Outcome Measures

Qualitative Study Outcomes:

i. In-depth semi-structured interviews with parents/caregivers who received the ECHO Intervention as part of their usual pathway of care.

ECHO Intervention Study Outcomes:

- i. Primary Outcome Measure: The Communication and Symbolic Behaviour Scales Developmental Profile™ (CSBS_DP) (Wetherby, A.; Prizant, B., 2002)
- ii. Secondary Outcome Measures, measured at baseline and 12-week follow-up (Parent-Child Interaction Pre/Post also taken at each intervention session)
- The Tool to Measure Parenting Self-Efficacy (TOPSE) (Bloomfield et al., 2010)
- Parent-Child Interaction Pre/Post Measure, a clinical tool used in current clinical practice to measure parent-child interaction strategy use
- WellComm Language Screen Toolkit Early Years Paper version (GL Assessments, 2015)
- The Pragmatics Profile of Everyday Communication Skills (Dewart, H., & Summers, S., 1995) to measure changes in child's communication skills

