4.3 Schedule of Procedures

Qualitative Study

Procedures	ECHO Intervention sessions 1-5 (Received as part of standard clinical practice*)	Review (Standard clinical practice 12 weeks after session 5)	Telephone call (At least 24 hours after review)	Interview (Within 12 months of session 5)**
Recruitment for Qualitative Study		X		
Telephone call to discuss participation queries			X	-
Interview			· ·	X

* Participants for the Qualitative Study do not need to participate in the ECHO Intervention Study

** Interviews will be conducted a minimum of 24 hours after Review session

ECHO Intervention Study

Department for Education

· · · · · · · · · · · · · · · · · · ·	ECHO Intervention Study visits (7)			
Procedures	Screening	Baseline (Minimum 24 hrs after screening)	ECHO Intervention sessions 1-5***	Review ^{****} (12 weeks after session 5)
Recruitment for ECHO Intervention Study	X		••••••••••••••••••••••••••••••••••••••	
Informed consent		Х		· ·
Demographics	· · · · ·	Х	· · · · · · · · · · · · · · · · · · ·	
All ECHO Intervention Study outcome measures collected		×		X
Parent-Child Interaction Pre/Post Measure completed		X	X	x

***May be conducted between 3 and 21 days after previous visit (including baseline visit)

****May be conducted up to 4 weeks before or after the 12-week window

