5.1.1 Inclusion Criteria

Qualitative Study:

- Parent/caregiver received at least one ECHO Intervention session within the last 12 months.
- Parent/caregiver residing within the Manchester Local Authority at the time of interview.
- Parent/caregiver having a sufficient level of oral language skills in any language to participate in an in-depth interview as assessed by the researcher's judgement.

ECHO Intervention Study:

- Parent/caregiver of a child aged less than 24 months at the start of intervention.
- Parent/caregiver of a child who scored Red on the WellComm Language Screen within 3 months of the start of intervention.
- Parent/caregiver of child who scored High Likelihood of autism on Social Attention and Communication Surveillance (SACS-R) tool.
- Residing within the Manchester Local Authority for the duration of intervention.

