Children will be referred to the Early Years Communication and Language Team by the Health Visiting Team following their 9-month Child Health Check offered to all families. Children may also be referred by Outreach Workers in the local children's centres following a WellComm Language Screen offered during Outreach support or whilst parents/caregiver_ attended the centre. Children referred to the Early Years Communication and Language Team will be screened for eligibility for the ECHO Intervention Study. These two referral pathways should increase the likelihood of low income and isolated families being referred as well as families reluctant to engage with medical services. Interpreters are available to referrers so that families with limited English skills may also receive support.

As part of standard practice, all children referred to the Early Years Communication and Language team who score Red on WellComm are offered screening with the Social Attention and Communication Surveillance Tool (SACS-R) unless:

- they have an identified visual or hearing difference,
- · they have identified motor differences other than delayed development,
- they have an identified developmental or medical condition that impacts social communication development, or
- there is concern that offering the SACS-R at this time may cause distress or harm.

Date: 16.05.2024

Manchester Local Care Organisation MANCHESTER CITY COUNCIL

Department for Education

Manchester University NHS Foundation Trust

As part of standard practice, children who score High Likelihood for autism on the SACS-R are referred for early communication intervention within the Early Years Communication and Language Service. Parents/caregivers of these children will be assessed by Speech and Language Therapists within the research team for their eligibility to participate in the ECHO effectiveness study. Speech and Language Therapists in the research team have access to patient details as part of standard clinical practice. A parent/caregiver's decision whether to participate in the study will not impact on the treatment options they will be offered or the treatment they will receive.

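### The WellComm analysis takes every child to be Red at baseline, which eligibility does not guarantee, so a child who left Red before session 1 can be reported as having progressed

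*Protocol*

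**What the plan says.** Section 6.1 (Data Analysis, ECHO Intervention Study) fixes three things about WellComm.

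- The starting point: "All children will score Red at baseline as this is part of the eligibility criteria".
- The quantity reported: "WellComm Screen results will be presented as the number and percentage (with 95% binomial confidence intervals) of children who score Red, Amber, and Green at" the review visit. No comparison with the baseline result is described.
- The reading: "Children scoring Amber or Green at review indicates that they have made clinically significant progress".

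The eligibility rule is in Section 5.1.1: "Parent/caregiver of a child who scored Red on the WellComm Language Screen within 3 months of the start of intervention". The flow chart gives the same window a different anchor: "Child Scored Red on WellComm Language Screen within 3 months of the referral".

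WellComm also appears as a measure taken at the baseline visit. Section 3.2 includes it among the "Secondary Outcome Measures, measured at baseline and 12-week follow-up". The schedule in Section 4.3 marks the row "All ECHO Intervention Study outcome measures collected" at Baseline and at Review, with Baseline at least 24 hours after Screening. The flow chart lists WellComm under the baseline visit.

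**The concern.** The Red result that makes a child eligible and the WellComm result obtained at the baseline visit are two different administrations. Section 6.1 treats them as one. These are children under 24 months, selected because they fell in the worst category of this same test. On re-test some may be out of Red through growth, measurement error or a change of assessor.

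A child who is Amber at the baseline visit and still Amber at review has not changed category during the study, yet the plan counts that child as having progressed. The baseline result that would show this is already due to be collected, but the WellComm analysis gives it no role. At stake is a single percentage under a clinical-progress label, in a study whose results go to funders who may disseminate them.

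**Working it through.** **Does eligibility make the premise true?**

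1. Section 5.1.1 allows the qualifying Red to be up to 3 months (about 13 weeks) before the intervention starts. Under the flow chart's referral anchor, no upper limit on the gap before session 1 is stated.
2. Section 5.4 places the Red result before the SACS-R is offered, and so before study screening. On one route it precedes referral: "Children may also be referred by Outreach Workers in the local children's centres following a WellComm Language Screen offered during Outreach support".
3. Section 4.2 has baseline and endpoint measures collected by Speech and Language Therapists in the research team, so the assessor may differ from whoever did the qualifying screen.
4. No exclusion criterion in Section 5.1.2 removes a child who is Amber or Green at the baseline visit, and nothing says that the eligibility screen stands in as the baseline value.

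The premise does not follow from the criteria.

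**Timing.** Sessions may be up to 21 days apart, so sessions 1 to 5 span at most 4 × 3 = 12 weeks. Review may fall up to 12 + 4 = 16 weeks after session 5. Under the Section 5.1.1 anchor the interval from screen to review can reach about 13 + 12 + 16 = 41 weeks, of which up to about 13 precede any session.

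**Evaluable number.** Section 5.3.1 gives 40 families and 10% dropout: 40 × 0.9 = 36. The protocol's only power figure reproduces at that number (paired t-test, two-sided 0.05, standardised effect 0.48: power 79.96%), but it concerns the primary outcome. There is no stated WellComm figure to reproduce.

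**Size of the error.** Let q be the share non-Red at the baseline visit, r the chance that such a child is non-Red at review, and p that chance for a child Red at the baseline visit.

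- Planned proportion = q·r + (1 − q)·p
- Proportion among children Red at baseline = p
- Difference = q(r − p)

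The protocol gives none of q, r or p, so every value below is an assumption.

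| q | r = 100%, p = 0 | r = 100%, p = 20% | r = 60%, p = 20% |
|---|---|---|---|
| 0 | 0 | 0 | 0 |
| 5% | 5 points | 4 points (24% v 20%) | 2 points |
| 10% | 10 points | 8 points (28% v 20%) | 4 points |
| 20% | 20 points | 16 points (36% v 20%) | 8 points |

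In whole children, the first column is about 2, 4 and 7 of 36: 5.6%, 11.1% and 19.4% reported as progress when nobody changed after baseline. For 4/36 the exact 95% interval would be 3.1% to 26.1%.

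**Per child.** One child non-Red at both baseline and review, with no other movement, gives 1/36 = 2.8% against 0/35. If 7 of the 35 others move, it gives 8/36 = 22.2% against 7/35 = 20.0%, a gap of 2.2 points. Hence up to 2.8 points per child.

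**Direction.** The difference is upward when r > p, which is likely. A child who goes Red, Amber, Red works the other way: with 7 movers among the other 35, the plan gives 7/36 = 19.4% against 7/35 = 20.0%.

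**Chance that the sentence is false.** If each child independently had a 5% chance of being non-Red at baseline (assumed), the chance of at least one among 36 is 1 − 0.95^36 = 84%; at 10% it is 98%.

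**The case against.** Four points can fairly be made for the plan.

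- **It is a minor outcome.** WellComm is one of several secondary measures, reported as percentages with intervals and no test, in a study that calls itself hypothesis generating. The primary CSBS DP analysis pairs actual baseline and endpoint scores. This stands, and it limits the severity.
- **Maturation is already disclosed.** Section 6.1 says it cannot be controlled for and that a randomised trial must follow. It also does not say that ECHO caused the movement. A reader might infer that the plan credits pre-intervention change to ECHO; the text stops short of that. The caveat still does not repair a statement about baseline that the criteria do not support and that scheduled data can check.
- **All variables will be described.** Section 6.1 promises descriptive statistics for every variable, which would cover the baseline WellComm result. Two separate distributions do not identify who moved, however. With 4 of 36 non-Red at baseline and 11 of 36 non-Red at review (illustrative), the number who left Red after baseline could be anywhere from 7 to 11 of the 32 who were Red. Nor is this merely detail left to an analysis plan: the protocol itself fixes the premise, the reported quantity and the reading.
- **The eligibility screen may be the intended baseline.** Then Sections 3.2 and 4.3 and the flow chart conflict with Section 6.1, and the reported change includes time before session 1. The text needs correcting either way.

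**Conclusion.** The statement in Section 6.1 that all children are Red at baseline is unsupported by the protocol's own criteria and schedule. Because the analysis rests on it, children who left Red before session 1 and stay out are misclassified as having progressed. The result would probably be an inflated figure for one secondary descriptive outcome. If every child is in fact Red at the baseline visit, there is no error.

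The size is unknown. Up to 2.8 points per affected child among 36 is an illustration, and the table above shows how far the total depends on assumed values.

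A reader might go further in two ways that the documents do not support. One is that the bias can only be upward: it equals q(r − p), so upward is likely but not certain. The other is that some 6 to 19 points of the reported progress would be spurious: that needs an assumed 5% to 20% out of Red at baseline, all of them still out at review, and no movement by anyone else.

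This is a wording and tabulation error that should be corrected. It does not threaten the study's main conclusion.

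**What to change.** In Section 6.1:

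1. Delete the sentence asserting that all children are Red at baseline.
2. Report the cross-tabulation of WellComm category at the baseline visit against category at review.
3. Give the proportion Amber or Green at review, with its 95% binomial interval, among children Red at the baseline visit.
4. State beside it that this proportion still includes regression to the mean and maturation, since it again conditions on the worst category.

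Reconcile the 3-month window in the flow chart (counted from referral) with that in Section 5.1.1 (counted from the start of intervention).

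Movement between the eligibility screen and the baseline visit may be tabulated, but should not be presented as an estimate of change without ECHO. The assessors may differ, the interval is not that from baseline to review, and every child starts Red by selection.

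The cost is wording. The baseline and review results are already scheduled, no visit or participant is added, and the denominator may fall by a few children.
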